NCTXXXXXXX

Adherence in Global Airways - Difference Between Structured and Systematic Nursing Supervison vs Usual Care.

Abbreviations

ACT - Asthma Control Test ACO-7 Asthma Control Ouestionnaire Adherence - Patients adherence to their non pharmacological/pharmacological treatment CRS -Chronic Rhinosi Chronic sinusitis CRSsNP - Chronic sinusitis with no nasal polyps CRSwNP Chronic sinusitis with nasal polyps ESS - EPWORTH SLEEPINESS SCALE Global Airways - Lower and upper respiratory diseases (asthma, rhinitis and CRS/CRSwNP/CRSsNP) HADS - Hospital Anxiety and Depression Scale MARS-5 - Medication adherence report scale MARS-5-L - Medication adherence report scale - lung MARS-5-N - Medication adherence report scale - nose miniAQLQ - Mini asthma quality of life questionnaire miniRQLQ - Mini Rhino conjunctivitis Quality of Life Questionnaire RCT - Randomised Controlled Trial SNOT-22 - The Sino-Nasal Outcome Test 22 STARR-15 - Standard test for asthma, rhinitis and chronic rhinosinusitis (15 questions) ENT - Department of Ear, Nose and Throat Surgery and Audiology, RigsHospitalet

Introduction

There is a strong case for treating diseases of both the upper and lower airways (global airways) simultaneously, because they share the same inflammatory mechanisms (1,2). About 9% have chronic sinusitis (CRS) and 4% of the Danish population are diagnosed with (CRS) with nasal polyps (CRSwNP) and 7-10% have asthma. CRS has a multifactorial background, with CRSwNP characterized by Type 2 inflammation, and approximately 50% with Type 2 CRSwNP also have co-morbid asthma (3). Well-treated CRS has an impact on asthma control, and well-treated asthma has an impact on CRS.

The above can be strongly supported by daily clinical practice, where these patients experience high levels of morbidity, which often significantly affect their daily lives and thereby also result in a markedly reduced quality of life. Several studies show that patients with asthma have low adherence (4,5), but only a few if any of studies are available on adherence in CRS. Patients rely on seeing different specialists (otolaryngologist and pulmonologist) to optimize their adherence in the upper or lower airways. This provides an opportunity

to investigate patients' adherence with diseases of the global airways, and analyse whether patients' adherence with diseases of the global airways can be improved and whether this will contribute to increased disease control and significantly improved quality of life.

Purpose

To investigate the effect of systematic and structured nursing guidance in patients with global airways disease, CRSwNP and asthma primarily on adherence (measured on MARS-5- L/N), where the maximum score is 50 at 100% adherence for both diseases. As well as whether there is a change at the minimum in adherence in patients who receive systematic and structured guidance on disease and treatment compared to usual care which does not include structured guidance.

Hypothesis and research questions

Patients with respiratory diseases can improve their adherence to their non-medical and the medical treatment for CRSwNP/CRS and asthma by systematic and structured nursing guidance compared to patients who did not receive the above guidance.

In a randomized study, we will investigate whether the level of adherence measured by the questionnaire MARS-5-N and MARS-5-L in patients with CRSwNP/CRS and asthma can be improved by 5 points after systematic and structured nursing guidance at baseline visit and controlled after four months - compared with those patients who have not received the above guidance.

Outcomes

The primary outcome is to investigate whether the adherence rate measured by the MARS-5-N/L questionnaire in patients with CRSwNP and asthma can be improved by 4 points after systematic and structured nursing guidance at the initial visit and controlled after four months - compared with those patients who have not received the above guidance.

Secondary outcomes

- To demonstrate whether improved adherence can improve their sleep measured on a Epworth Sleepiness Scale - messured during a 4 month follow-up visits.

- To demonstrate whether improved adherence can improve their SNOT22 score by 9 points or more messured at a 4 month follow-up visits.

- To demonstrate whether improved adherence can improve their asthma control as measured by the ACQ messured at a 4 month follow-up visits.

- To demonstrate whether improved adherence can improve their asthma control as measured by ACT - measured at a 4 months follow-up visit.

- To demonstrate whether improved adherence can improve their quality of life as measured by the mini AQLQ messured at a 4 months follow-up visit.

06.05.2022

- To demonstrate whether improved adherence can improve their anxiety/depression as measured by HADS - messured at a 4 months follow-up visit.

- To demonstrate whether satisfactory adherence (i.e. 80%) can improve their nasal symptoms measured via SNOT22 and STARR-15 - messaured at 4 a months follow-up.

- To demonstrate whether satisfactory adherence (i.e. 80%) on lung measured via MARS-5-L and poor adherence on nose measured via MARS-5-N improve their respiratory symptoms measured ACQ or ACT - messsured at a 4 months follow-up.

- Demonstrate differences in patients with three conditions (asthma, CRS and allergic rhinitis) measured via STARR-15 meassured at a 4 months follow-up visit.

Background

CRS is a condition of chronic inflammation of the nose and sinuses. CRS can appear in the nasal polyps (CRSwNP) and without polyps (CRSsNP)(2,3). 9% of the Danish population is affected by CRS, and approximately 4% are estimated to be diagnosed with CRSwNP (4). The diagnosis is based on the patient's symptoms and objective signs of inflammation in the nose and sinuses. Symptoms include nasal congestion or nasal secretion that runs forward or backward, decreased air passage, decreased sense of smell, pain/pressure around the nose, forehead or eyes. For the diagnosis to take place, the above symptoms must have been present for more than 12 weeks. To diagnose CRS, there must be secretions or reduced air passage through the nose (6,7). Approximately 40% of CRS patients in primary care have asthma, whereas 65% referred to hospital have asthma (8).

CRSwNP that is not satisfactorily controlled has a significant impact on quality of life (9,10). It is often characterized by type 2 inflammation, i.e. increased numbers of eosinophils in the mucosa of the sinuses and nasal polyps - as well as comorbidities e.g. asthma, ASA/NSAID intolerance (N-ERD) and allergies (3). CRSwNP can be treated both surgically and medically. Basic medical treatment of CRS includes daily saline irrigation and application of nasal steroid. In the case of nasal polyps, systemic steroid (tbl. prednisolone/inj. betamethasone) may be added as a course, and never as a fixed treatment (3,6). Some patients receive 1, 2 or 3 courses annually for several years, which is accompanied by many systemic side effects (1,2,11). If medical treatment is not optimal, patients may be offered surgical treatment -endoscopic sinus surgery (ESS)(2,3). The goal is the removal of polyps in the nose and sinuses, to create better air passage.

Comorbidity

In patients with CRS, attention should also be paid to comorbidity due to the interplay between the upper and lower airways. Patients with uncontrolled CRSwNP often suffer from a high burden of disease (9). Asthma and CRSwNP often interact negatively. Therefore, patients should also be evaluated for asthma. Patients with CRSwNP and type-2 inflammation (high eosinophil cell count in the blood or mucosa of the nose) are

more likely to have recurrence of CRSwNP after surgery than patients with low eosinophil cell count (3). Patients with asthma may also experience more rapid recurrence of their polyps after surgery than patients who do not have asthma.

Asthma

Asthma is a chronic inflammatory respiratory disease. It is characterized by chronic airway inflammation, airway hyperactivity and variable airway obstruction (12). It is estimated that over 300 million people worldwide suffer from asthma, of wichic most are born and raised in the Western world, which has a major impact on the economy (5). Symptoms of asthma include coughing, wheezing, shortness of breath, chest tightness, etc., and can vary in intensity. The diagnosis is made on the basis of disease history and objective findings, e.g. spirometry, FeNO measurement, provocation tests, and peak flow test (12).

Adherence

The term adherence describes the patient's compliance with the treatment strategy developed in consultation with a practitioner. The patient is considered an active participant in his or her treatment. Adherence can be measured for both pharmacological and non-pharmacological treatment. The WHO classifies measures of adherence as subjective and objective (13,14). Objective measures include measures such as pill counts, electronic monitoring (common medical card) or biochemical measures (e.g. blood tests) (13). Subjective measures include those that require assessment by, for example, the doctor, nurse or patient. Self-reporting by the patient or assessment by the healthcare professionals are the most common methods used to assess patient adherence. MARS-5 is a subjective tool that can be used to measure patient adherence - developed by [name] (15,16). The MARS-5 is a generic tool. It has been validated in many different clinical settings, e.g. in patients with asthma (17). The MARS-5 consists of five questions describing patient adherence to their medical treatment. Question 1) "I forget to take them", question 2) "I change the dose", question 3) "I stop taking them for a while", question 4) "I decide to skip a dose" and question 5) " I take less than instructed". Patients are asked to rate their adherence to their medication on a 5-point scale ranging from "always" to "never" (1-5 points). The total score on the scale goes from 5 (lowest compliance) to 25 points (macsi-mal compliance).

Poor adherence is particularly seen in long-term treatment among chronic patients, underlining the importance of focusing on sustained adherence in these patients (18). Some patients stop their treatment when they have symptoms under control, after which an exacerbation occurs. They resume their treatment with the feeling that "it is not helping" because they get worse (19). The WHO estimates that only 50% of patients receiving long-term pharmacological treatment for their chronic diseases are adherent to their treatment (19,20). Adherence in asthma and COPD has been shown to vary between 22%-78% (5,19). Patients with asthma receive information, guidance, and training related to their disease in the context of "usual care" in many places. Patients' adherence to pharmacological treatment depends on their age, their level of education, their knowledge of asthma, how often they have to take medication, whether the medication is easy to take,

and how their communication is with the practitioner (19,20). Adherence to inhaled medications is lower than to oral tablets or injectable medications. The more complex and the more times the patient has to remember to take the medication, the harder it is to establish optimal adherence (19,20).

CRSwNP a chronic disease like asthma, where low adherence is often seen in mild to moderate cases compared to severe cases of CRSwNP (21). However, the clinical perception is that not all patients take all their daily doses, but few scientific studies have focused on this. The difficulty in treating CRS is that the patient must apply nasal steroid 1-2 times daily as well as it must be combined with nasal saline irrigation at least once daily. Decreased adherence is led by poor disease control. It is therefore important to support and strengthen patient adherence to CRS and asthma in order to achieve good disease control (21).

Population and recruitment

The study population consists of patients referred to the Respiratory Clinic in the Department of Ear, Nose and Throat Surgery and Audiology, Rigshospitalet. Patients are recruited by initial visits to the Respiratory Clinic, where they receive oral and written information about the project. If patients wish to participate, they must complete a written consent form for participation in the project. In order to be included in the study, the following inclusion and exclusion criteria must be met:

Inclusion criteria	Exclusion criteria
Adherence to MARS- 5 L/N ≤35	Adherence to MARS-5- L/N >35
at first visit	points at first visit
Diagnosed with asthma (with and	Do not have smartphone
without allergic rhinitis) at initial	
visit	
Able to use smartphone	Does not read or speak English
Able to use smartphone	Does not read of speak Elignish
ACQ \geq 1.2 or ACT \leq 15 (partially	Other illness requiring regular
uncontrolled asthma)	medication
Be over 18 years of age	Pregnancy and pregnancy that
	started during the study time pe-
	riod
SNOT-22 score ≥35	Servere psychological comorbidi-
	ties
Diagnosed with CRSwNP	

Material and method

The study is a randomized trial with a control group and an intervention group. Patients will be randomized via Research Electronic Data Capture (Redcap), a secure web application for building and managing databases and online questionnaires. The system was developed at Vanderbilt University, which released the first version in 2008 (22). Patients will be randomized to the control or intervention group. Randomization will be stratified by gender. Patients in the intervention group will receive systematic and structured nursing guidance regarding their adherence, which includes proper use of nasal irrigation once or twice daily, nasal steroid/drops, use of inhaled medications, follow-up of smoking status. The intervention group will receive guidance videos which have been prepared prior to the study and will be standard for the intervention group. Guidance videos will cover the correct use of nasal irrigation, inhalation steroid, and nasal steroid/drops. The control group and intervention group will receive twice a week text message reminders to take their medications and to rinse their nose.

Their adherence will be measured via MARS-5-N and MARS-5-L f. Total MARS-5-N/L will be measured at their initial visit and four months after teaching or usual care. The same form will be given at both visits. Patients in the control group will not receive systematic and structured nursing care regarding their adherence, but their adherence will be measured via MARS-5-N and MARS-5-L max score is 50 when measuring a adherence in global airways. In a pilot study, mean (SD) 20.4 (6.28) is found for MARS-5-L, and for MARS-5-N mean 20.7 (5.57) is found. 41 points correspond to 80% of total of both MARS-5-L and MARS-5-N. A satisfactory adherence should be 80%. In another pilot study, patients were measured twice with at least one month in between. Here, the mean of the inter-individual difference at MARS-5-L/N first and second time is equal to 5.34(2.62). These two pilot studies will be used for the final power calculation.

Statistics data analysis and power calculation

The statistical analysis of data is performed using IBM SPSS Statistics. Results will be presented as mean, SD, range and 95% CI. The parametric data will be compared using paired and unpaired tests, and non-parametric data using Wilcoxon Signed-Ranks Test and Mann-Whitney Test, respectively. Categorical variables are tested by chi-square test. A P-value <0.025 is considered significant for a pooled MARS-5-N and MARS-5-L For a pooled MARS5-L/N questionnaire, the total score would be 25x2= a total of 50 points theoretically. A safe difference is calculated from the intraindividual difference detected in the pilot study (mean 5.34 (2.62)), but based on the pilot study an SD and mean are calculated on the difference between MARS-5-L/N, which corresponds to an SD 5.34 and mean 2.62. With a MIREDIF of 5 and the largest SD of 6.28 by single measurement with a p-value of 0.025% (0.05/2) because there are two schedules and a power 80%, this would require 36 patients in each group including a dropout of 20%.

In addition, ensuring that MARS-5-N/L are both above 80% (the standard requirements for good adherence); and hoping for 100% adherence in the intervention group, versus 80% in the control group, this would require 39 in each group. - And including the 20% dropout rate, the total population would be 47 in each group.

Project participants

[name], nurse, Department of Otolaryngology and Audiology

[name], clinical nurse specialist and ph. Student, Department of Ear, Nose and Throat Surgery and Audiology

[name], Senior Physician, Department of Ear, Nose and Throat Surgery and Audiology

[name], Professor, MD, Department of Ear, Nose and Throat Surgery and Audiology

Risks and side effects

There are no serious side effects associated with participation in the trial. There may be a risk that patients in the control group of the study may have a worse prognosis/prognosis than patients achieving good adherence (80%) in the intervention group. To reduce this risk, patients in the control group are offered the same guidance as those in the intervention group at the end of the trial.

Information from patient records

No personal data will be collected from patient records. Data included in the study are from patient questionnaires and from results of clinical objective tests.

Processing of personal data

The project is carried out in compliance with the Data Protection Regulation and the Data Protection Act.

Economy

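### The primary outcome targets a 4-point gain on MARS-5-N/L, but the research question and the mean-difference sample size use 5 points, and the stated 80% power was calculated only for 5

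*Combined protocol and SAP*

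**What the plan says.** All references are to the combined protocol and SAP.

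- **Hypothesis and research questions:** the trial will examine whether adherence on MARS-5-N and MARS-5-L "in patients with CRSwNP/CRS and asthma can be improved by 5 points after systematic and structured nursing guidance at baseline visit", checked at four months against patients without guidance.
- **Outcomes:** the primary outcome is whether adherence on MARS-5-N/L "in patients with CRSwNP and asthma can be improved by 4 points after systematic and structured nursing guidance at the initial visit", also checked at four months against patients without guidance.
- **Population and recruitment:** there is a single set of entry criteria, which includes "Diagnosed with CRSwNP".
- **Material and method:** one combined score is taken twice: "Total MARS-5-N/L will be measured at their initial visit and four months after teaching or usual care". Its maximum is 50. The pilot results are "mean (SD) 20.4 (6.28) is found for MARS-5-L, and for MARS-5-N mean 20.7 (5.57) is found".
- **Statistics data analysis and power calculation:** the mean-difference calculation begins "With a MIREDIF of 5 and the largest SD of 6.28 by single measurement". With a p-value of 0.05/2 and 80% power it arrives at 36 per group, including 20% dropout. A second calculation, 100% against 80% adherence, gives 39 per group, or 47 with dropout. Significance for the pooled score is set at P<0.025.

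**The concern.** The two targets stand in adjacent sections and concern the same contrast, questionnaire and time point. Nothing in the plan explains why they differ.

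The choice of target matters in two ways. First, an observed difference between 4 and 5 points meets the target in Outcomes and misses the one in the research question, and nothing fixed in advance says which applies. Second, the primary outcome is the statement the trial will be held to. If 4 points is the real target, a reader would take the stated 80% power as covering it, although that figure was worked out for 5.

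**Working it through.** **Could the two numbers describe different things?** One sentence says CRSwNP/CRS and the other CRSwNP, but the entry criteria define one population and require CRSwNP. One names the two scales and the other writes N/L, but Material and method measures one total at both visits. If 5 was meant per scale and 4 for the total, the plan does not say so, and the 4-point primary outcome would still have no power calculation.

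**Inputs.** SD 6.28, difference 5, alpha 0.025, power 80% and 20% dropout come from the statistics section. The test is taken as two-sided with equal groups. Sidedness is not stated, but two-sided reproduces the plan's 36, whereas one-sided 0.025 gives 25, or 30 with dropout.

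**The plan's 36.** n per group = 2(z₀.₉₈₇₅ + z₀.₈₀)²(SD/difference)²

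- 5 points: 2(2.241 + 0.842)²(6.28/5)² = 29.99, so 30; 30 × 1.2 = 36. This matches.
- 4 points, same inputs: 2(2.241 + 0.842)²(6.28/4)² = 46.86, so 47 (49 by t-test); 47 × 1.2 = 56.4, so 57. The stated 36 therefore fits 5 points and not 4.

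**The plan's 47.** For proportions 0.80 and 1.00, (3.083)²(0.80 × 0.20 + 1.00 × 0)/(0.20)² = 38.02, so 39; 39 × 1.2 = 46.8, so 47. No point difference enters this calculation, so it supports neither target.

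**Evaluable numbers.** With 36 enrolled: 36 × 0.8 = 28.8, taken as 29, or 36/1.2 = 30. With 47 enrolled: 47 × 0.8 = 37.6, taken as 37, or the stated 39.

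**Power at two-sided 0.025** (noncentral t / normal approximation):

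| Difference | SD | n=29 | n=30 | n=37 | n=39 |
|---|---|---|---|---|---|
| 5 | 6.28 | 0.765 / 0.785 | 0.781 / 0.800 | 0.869 / 0.882 | 0.888 / 0.899 |
| 4 | 6.28 | 0.552 / 0.573 | 0.568 / 0.589 | 0.674 / 0.691 | 0.700 / 0.716 |
| 4 | 5.57 | 0.667 / 0.689 | 0.684 / 0.705 | 0.786 / 0.802 | 0.810 / 0.824 |
| 4 | 5.34 | 0.708 / 0.729 | 0.725 / 0.745 | 0.822 / 0.837 | 0.844 / 0.857 |
| 4 | 8.39 | 0.320 / 0.335 | 0.332 / 0.346 | 0.410 / 0.424 | 0.432 / 0.445 |
| 4 | 11.85 | 0.163 / 0.170 | 0.168 / 0.175 | 0.208 / 0.215 | 0.219 / 0.226 |

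**Where the SDs come from.**

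- 6.28 is the pilot SD of MARS-5-L alone, and the one the plan sizes on. 5.57 is that of MARS-5-N.
- 5.34 is the SD of the repeat-measurement difference as the statistics section labels it ("which corresponds to an SD 5.34 and mean 2.62"). Material and method labels the same pair the other way round, with 2.62 as the SD; at 2.62 power for 4 points exceeds 99%.
- 8.39 and 11.85 bracket the SD of the 50-point total, which is not given: √(6.28² + 5.57² + 2r × 6.28 × 5.57) with an assumed lung–nose correlation r of 0 and 1. At these SDs power for 5 points is also low: about 25–53% with 36 enrolled and 32–65% with 47.

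**Smallest observed difference reaching P<0.025** (t-test, over the four group sizes): 3.25–3.80 points at SD 6.28; 4.35–5.08 at SD 8.39; 6.14–7.17 at SD 11.85.

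**The case against.** The strongest reply is that little turns on this. The plan's criterion is P<0.025, and neither target changes that test. At the planning SD any observed difference between 4 and 5 points would be significant. No passage makes either number a success rule, and the 36 is correctly calculated. All of this stands, and it limits the harm to interpretation and to the power statement.

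A second reply is that the size of the shortfall is uncertain. Power for 4 points runs from about 16% to over 99% depending on the SD, and most of that spread comes from a different weakness: a single-scale SD used for a pooled total. The plan also leaves open whether the between-group test uses four-month scores or change from baseline. In addition, the pilot SDs may not describe the enrolled patients: the pilot means sum to 20.4 + 20.7 = 41.1, while entry requires a score of 35 or less. These points also stand. They make the like-for-like comparison at SD 6.28 the one to rely on, and they mean that 80% for 5 points is not established for the total either. None of them explains why two targets are printed.

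**Conclusion.** The concern holds. The plan contradicts itself on its primary target, and its 80% power was calculated for 5 points, not for the 4 points in the primary outcome. This is an inconsistency, not a miscalculated figure.

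On SD 6.28 and two-sided alpha 0.025, power for 4 points is about 55–59% with 36 enrolled per group and 67–72% with 47, against 76–80% and 87–90% for 5 points. For 4 points, power falls below 80% at both sizes for SD 6.28 or larger, but not at every SD the plan prints: with 47 enrolled it is 79–82% at SD 5.57 and 82–86% at SD 5.34. The contradiction itself depends on none of these assumptions. It should be fixed before results are read.

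**What to change.** Use one target difference in the research question, the primary outcome and the power section.

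- **Simplest:** change 4 to 5 in Outcomes, matching the difference already used for sizing.
- **If 4 is intended:** change the research question to match, keep the planned size, say whether that is 36 or 47 per group, and restate the power for 4 points using the SD of the score actually analysed. The 80% should not be carried over.

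The cost is one number, or a matching number and one restated power figure if 4 is kept. Design, enrolment and the test at P<0.025 do not change. Moving to 5 removes the contradiction but does not show that power is 80% on the 50-point total; the SD of that total is a separate matter that still needs to be stated.

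### The primary outcome asks for an improvement of 4 points (5 in the research question), but P<0.025 from a test of no difference can support only that adherence improves, not by how much

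*Combined protocol and SAP*

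**What the plan says.** - **Outcomes (primary).** The question is whether adherence on MARS-5-N/L "can be improved by 4 points after systematic and structured nursing guidance at the initial visit", with follow-up at four months and comparison with patients who did not get the guidance.
- **Hypothesis and research questions.** The opening sentence has no threshold: patients can improve their adherence "by systematic and structured nursing guidance compared to patients who did not receive the above guidance". The research question that follows asks whether adherence "can be improved by 5 points after systematic and structured nursing guidance at baseline visit". The Purpose section also mentions a minimum change, without a number.
- **Statistics data analysis and power calculation.** The rule is "A P-value <0.025 is considered significant for a pooled MARS-5-N and MARS-5-L". On the tests: "The parametric data will be compared using paired and unpaired tests", with Wilcoxon and Mann-Whitney tests for non-parametric data. On reporting: "Results will be presented as mean, SD, range and 95% CI".
- **The same section, sample size.** The 5 points appears as the MIREDIF, with SD 6.28, a level of 0.05/2, 80% power and 36 per group after a 20% dropout allowance. A second calculation, on proportions, gives 39 per group, or 47 with dropout. The 4 points appears in neither.
- **Secondary outcomes.** One asks whether better adherence can "improve their SNOT22 score by 9 points or more".

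No null value of 4 or 5, confidence-limit rule, threshold for the estimate or responder definition is linked to these numbers.

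**The concern.** As worded, the primary outcome is a question about the size of the benefit over control. The decision rule answers a different question, namely whether there is any difference. Rejecting a null of zero does not establish a difference of 4 or 5 points. If the report answers the primary question from the P-value, it can state a benefit of 4 points when the interval reaches well below 4. The planned 95% CI does not settle this: nothing says how it is to be read against the target, and it is narrower than the interval that corresponds to a test at 0.025. Choosing between 4 and 5 would not cure the mismatch, although the rule needs one value before it can be applied.

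**Working it through.** **1. Which null the plan uses.** The plan does not state it in words, so I infer it from the named tests and from the sample size. Inputs from the statistics section: difference 5, SD 6.28, level 0.025 (printed with a percent sign, but 0.05/2 = 0.025), power 80%. Assumed: two-sided, equal groups, null of zero.

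n per group = 2 × SD² × (z₀.₉₈₇₅ + z₀.₈₀)² / difference² = 2 × 6.28² × (2.241 + 0.842)² / 5² = 30.0

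30 × 1.2 = 36, the stated figure. (Dividing by 0.8 gives 38.) A one-sided 0.025 level gives 25, hence 30 to 32 with dropout, which does not match. For contrast, a literal test against 4 points with a true difference of 5 leaves a margin of 1 point and needs 750 per group before dropout. The plan is therefore an ordinary superiority design.

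**2. Where significance starts.** Assumption: 39 analysed per arm, the pre-dropout figure from the second calculation. Smallest significant observed difference = t₀.₉₈₇₅,₇₆ × SD × √(2/39), with t = 2.287.

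- SD 6.28: 2.287 × 6.28 × 0.2265 = 3.25 points.
- With other numbers analysed at the same SD: 3.73 points at 30 per arm and 2.95 at 47.

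**3. The pooled score.** The Material and method section gives 6.28 as the pilot SD of MARS-5-L alone and 5.57 for MARS-5-N. It gives no SD for the 50-point sum. With an assumed correlation ρ between the scales, SD = √(6.28² + 5.57² + 2ρ × 6.28 × 5.57). At 39 per arm:

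| SD | Basis | Significance starts at | Observed difference needed for lower 97.5% limit = 4 |
|---|---|---|---|
| 6.28 | plan's value | 3.25 | 7.25 |
| 8.39 | ρ = 0 | 4.35 | 8.35 |
| 10.27 | ρ = 0.5 | 5.32 | 9.32 |
| 11.85 | ρ = 1 | 6.14 | 10.14 |

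The last column is 4 plus the column before it.

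**4. What the interval shows at that edge.** The 97.5% CI is the observed difference ± the same critical amount, so its lower limit is 0 in every row. At SD 6.28 it runs from 0 to 6.5. The planned 95% CI uses t = 1.992 and a half-width of 2.83, so its lower limit is 3.25 − 2.83 = 0.42. Neither interval comes near excluding differences below 4.

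**5. How often the stronger claim would be available.** At SD 6.28, 39 per arm and a true difference of 5, the chance that the lower 97.5% limit exceeds 4 is about 6%.

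**The case against.** The strongest reply is that 4 and 5 are only target differences. The statistics section calls 5 the MIREDIF, the opening hypothesis sentence has no threshold, and a superiority trial need not test against its planning difference. On that reading the design is conventional. This largely stands for the 5 points, and it is why the remedy concerns wording and not design. It does not clear the primary outcome: the 4 points stands in the outcome definition itself and is used in neither sample size calculation.

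It can also be said that any superiority trial has an interval touching zero at the edge of significance, and that the plan promises means and a 95% CI, so readers would see the uncertainty. Both are true. But the issue is what may be concluded, and the plan gives the interval no part in that.

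Four stronger readings are tempting and are not supported:

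- *The trial will declare success at observed differences below its target.* That rests on 6.28, a single-scale SD. With the pooled SDs above and 39 per arm, significance starts above 4 points throughout, and above 5 at the higher correlations.
- *The trial should be powered to exclude 4 points.* Nothing in the documents sets that aim.
- *A rank test would leave no result in points.* Its P-value is not a test of a mean difference in points, but means and CIs are promised in general.
- *SNOT-22 has the identical fault.* The 0.025 rule is stated for the pooled MARS score only, and the SNOT-22 outcome is not clearly a between-arm contrast: its 9 points could be a within-patient threshold.

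**Conclusion.** The concern holds as a mismatch between the primary question and the conclusion that the test permits. P<0.025 alone can support the statement that guidance improves adherence. It cannot support an improvement of 4 or 5 points, whatever the SD. Whether a significant result could fall below the target in observed points is uncertain: the edge is 3.25 points at SD 6.28, and 4.3 to 6.1 if the pooled SD is 8.4 to 11.9. These figures assume 39 analysed per arm, a two-sided 0.025 level, a t-test and, for the pooled SD, a correlation of 0 to 1. The null of zero is inferred, but 36 per group reproduces with it. Sample size and choice of test are not faulted on this point. The change is worth making before analysis because it determines what the trial may claim.

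**What to change.** - Reword the primary outcome as the between-arm difference in mean pooled MARS-5-N/L at four months, tested against zero.
- Reconcile 4 and 5 into one value and label it as the planning (minimum relevant) difference.
- Report the difference with a 97.5% CI, which matches the 0.025 level.
- State two levels of conclusion. P<0.025 supports an improvement in adherence. An improvement of at least the target may be claimed only if the lower 97.5% limit reaches the target.
- For SNOT-22, first state whether the 9 points is a between-arm mean difference or a within-patient threshold, and do not claim it from a P-value alone.

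The cost is wording only: no added patients, visits or data. The downside is that the stronger claim will rarely be available. For a 4-point target it needs about 7.25 observed points at SD 6.28 and 39 per arm, and more if the pooled SD is larger.
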